The end of the Maintenance Period will be Visit 9, or, if subjects withdraw early, the Early Termination Visit. Subjects may be eligible for participation in an additional open-label study (SP848) if they have completed the Maintenance Period and are taking a minimum dose of 4mg/kg/day for subjects weighing <50kg or 200mg/day (tablets/oral solution) for subjects weighing ≥50kg. Subjects who do not complete the full 12 weeks of the Maintenance Period may still be eligible to enter the SP848 open-label study after consultation with the medical monitor. Subjects who choose not to participate in the additional open-label study or subjects who discontinue LCM due to other reasons will enter a 2- to 4-week Taper Period followed by a Safety Follow-Up Visit 2 weeks (±2 days) after the final dose of LCM and a Safety Follow-Up Telephone Contact 30 days (-1/+3 days) after the final dose of LCM. Taper of LCM may not be required for some subjects who discontinue study medication prematurely, depending on the treatment option selected by the investigator in consultation with the subject and/or parent/legal representative.

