The study will begin with subject screening at Visit 1 and will consist of a 6-week prospective Baseline Period where seizure frequency will be captured. Subjects/caregivers will maintain a diary to record daily seizure activity from Visit 1 until the end of the study. The subject diary will capture seizure type and seizure frequency information. If all inclusion criteria are met and no exclusion criterion is met, the subject will begin a 6-week Titration Period (LCM dosing flexibility allowed based on tolerability) starting at Visit 2. Subjects will be asked to return to the clinic on the morning of the day prior to Visit 2 to begin 24-hour ambulatory EEG recordings. Subjects will initiate treatment with LCM oral solution at 2mg/kg/day, or LCM tablets at 100mg/day based on body weight. The dose will be titrated to a level to optimize tolerability and seizure control, not to exceed 12mg/kg/day (oral solution) for subjects weighing < 50 kg, or 600mg/day (tablets/oral solution) in subjects weighing ≥ 50 kg. Subjects will increase the LCM dose in a stepwise fashion on a weekly basis to optimize tolerability and seizure control (see Figure 5-1 and Figure 5-2).

Lacosamide doses will be titrated according to the schedules presented in Table 7-1 and Table 7-2.

At the end of the Titration Period (Visit 6), a 12-week Maintenance Period will begin. The LCM dose will remain stable throughout the Maintenance Period. Subjects who require a change in dose during the Maintenance Period will be withdrawn from the study. Subjects who require a change in formulation during the Maintenance Period should consult the medical monitor to assess if the subject can continue in the study.

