#### **3.2 General study level definitions**

##### **3.2.1 Last dose of LCM**

Unless otherwise noted, all references to the last dose of LCM in this SAP refer to the last dose of LCM within the study (eg, including the Taper Period). The last dose of LCM during the Treatment Period will be defined as the last dose during the Titration and Maintenance Periods.

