### 3.2.3 Study periods

For the purpose of analyses, the following periods are defined.

- Baseline Period:

The Baseline Period is defined as the period of time from the date of Visit 1 to 1 day prior to the date of first dose of LCM. For the definition of Baseline values see Section 3.3.

- Titration Period:

The Titration Period is defined as the period of time from the date of first dose of LCM to the date of Visit 6 or the date of ET, whatever occurs first. If Visit 6 and ET are missing the Titration Period ends at the date of last dose of LCM.

- Maintenance Period:

The Maintenance Period is defined as the period of time from the day after the date of Visit 6 to the date of Visit 9/ET. If Visit 9/ET is missing the Maintenance Period ends at the date of last dose of LCM.

- Treatment Period:

The Treatment Period is defined as the combined Titration and Maintenance Period, ie, starts at the date of first dose of LCM and ends at Visit 9/ET. If Visit 9/ET is missing the Maintenance Period ends at the date of last dose of LCM.

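### When the closing visit is missing, SAP 3.2.3 ends Maintenance (or Titration) at a last dose that includes the Taper, so a subject who misses the visit but still tapers has taper days counted in the wrong period

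*SAP*

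**What the plan says.** SAP 3.2.3 closes the Maintenance Period at Visit 9/ET and adds a fallback: "If Visit 9/ET is missing the Maintenance Period ends at the date of last dose of LCM". The Treatment Period definition repeats that sentence. The Titration Period has a parallel rule: "If Visit 6 and ET are missing the Titration Period ends at the date of last dose of LCM".

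SAP 3.2.1 fixes what the phrase means. Except where the SAP says differently, its mentions of that dose "refer to the last dose of LCM within the study (eg, including the Taper Period". Section 3.2.3 states no exception. Section 3.2.1 also offers a narrower term: "The last dose of LCM during the Treatment Period will be defined as the last dose during the Titration and Maintenance Periods". Section 3.2.3 does not use it.

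The protocol has no last-dose fallback. Its Summary says: "The end of the Maintenance Period will be Visit 9, or, if subjects withdraw early, the Early Termination Visit". Protocol 5.1 says of dosing: "The LCM dose will remain stable throughout the Maintenance Period". Protocol 8.4 places the Taper in a separate End of Study Period. SAP 3.9 declares no change to the protocol-defined analyses.

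**The concern.** Read together, SAP 3.2.1 and 3.2.3 tell the programmer to extend the period through the Taper whenever the closing visit is missing. The narrower term in 3.2.1 would not solve this. It refers to the last dose in Titration and Maintenance, and in exactly this case the end of those periods is what has to be found.

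No later section removes the taper days:

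- **Seizure days (SAP 8.1.2, a primary variable).** Seizure days and diary days are both counted within the study period. For Titration dropouts, SAP 4.2.2 carries the Titration estimate forward as the Maintenance value, so any taper days in it go along.
- **Mean daily Maintenance dose (SAP 8.4).** Dosing records are cut only at the Maintenance end date, which is the date in error.
- **Exposure duration (SAP 8.4).** It is derived per period and lengthens with the period.
- **TEAEs by period (SAP 8.2.2).** Taper events move into the Titration or Maintenance table.
- **Treatment Period window.** It defines Last Visit (SAP 3.2.4) and the treatment-emergent laboratory and ECG abnormalities (SAP 8.5, 8.6.2). Assessments made during the Taper could be reported as on-treatment values.

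**Working it through.** **Inputs.** Maintenance length: "a 12-week Maintenance Period will begin" (Protocol 5.1). Taper length and weekly doses: Protocol Table 7-4, from 2 weeks (3-4 mg/kg/day) to 4 weeks (7 mg/kg/day and above). Dose formula: SAP 8.4. Seizure formula: SAP 8.1.2, seizure days × 28/D, where D counts only days with seizure information.

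**1. The plan's own figure.** 12 weeks × 7 = 84 days, which matches the boundary of the top Maintenance exposure category (more than 84 days) in SAP 8.4. With a 28-day taper added, the derived period is 84 + 28 = 112 days.

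**2. Taper share and mean dose.** With M Maintenance days and T taper days, the taper share is T/(M + T). The derived mean dose is (dose × M + 7 × sum of weekly taper doses)/(M + T).

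| Maintained dose (taper by week), mg/kg/day | M | T | Taper share | Derived mean dose |
|---|---|---|---|---|
| 12 (9, 6, 4, 2) | 84 | 28 | 28/112 = 25% | (1008 + 147)/112 = 10.31 (-14.1%) |
| 12 (9, 6, 4, 2) | 28 | 28 | 28/56 = 50% | (336 + 147)/56 = 8.63 (-28.1%) |
| 12 (9, 6, 4, 2) | 14 | 28 | 28/42 = 67% | (168 + 147)/42 = 7.50 (-37.5%) |
| 4 (2, 2) | 84 | 14 | 14/98 = 14.3% | (336 + 28)/98 = 3.71 (-7.1%) |
| 4 (2, 2) | 28 | 14 | 14/42 = 33.3% | (112 + 28)/42 = 3.33 (-16.7%) |

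Every scheduled taper dose is below the maintained dose, so the derived mean always falls. In the last two rows it falls below 4 mg/kg/day, the protocol's minimum for entering Maintenance. If the period ended at the last pre-taper dose, the mean would equal the stable dose.

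**3. Seizure days per 28 days.** The documents give no rates. Assume Baseline 10, Maintenance 8 (a change of -2.0), and 28 taper days that all have diary data. With a taper rate r, the derived value is (24 + r)/4 after 84 Maintenance days and (8 + r)/2 after 28.

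| Taper rate r | Change, 84 + 28 days | Change, 28 + 28 days |
|---|---|---|
| 4 | -3.0 | -4.0 |
| 8 | -2.0 | -2.0 |
| 12 | -1.0 | 0.0 |
| 16 | 0.0 | +2.0 |

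The shift is zero if the taper rate equals the Maintenance rate, and otherwise can go either way.

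**4. Group level.** Assume all 50 subjects contribute. One subject like the 28-day, 12 mg/kg/day case moves the overall mean dose by 3.375/50 = 0.07 mg/kg/day. The most adverse seizure case above (+4 days) moves the overall mean by 4/50 = 0.08 days per 28 days. In an age group of 10 the seizure shift is 4/10 = 0.4. In a syndrome subgroup of 4, the smallest that SAP 4.8 will present, it is 4/4 = 1.0.

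**The case against.** The strongest reply is that the trigger is rare. The subject must miss Visit 9/ET and still take a taper. Taper drug and the taper diary are dispensed at Visit 9/ET (Protocol 8.3.4), and subjects who stop without tapering are also asked to attend it. Someone with no such visit has more probably stopped attending than followed a site-managed taper. If no taper is taken, the last dose in the study is the last Maintenance dose and the fallback works. Tapering from supplies already held is possible, but would be an exception. This stands, and it limits the size of the problem.

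Several stronger inferences are tempting but not supported:

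- **That early leavers in general are affected.** Those with an ET visit have their period closed on that date under SAP 3.2.3. Only those missing the visit are exposed. Taper may also be omitted after premature discontinuation, and low doses need none (Protocol 7.2).
- **That taper days necessarily enter the primary seizure variable.** D excludes days without seizure information, and without Visit 9/ET the taper diary is not issued on schedule.
- **That total TEAE counts are inflated.** Events up to 30 days after the last dose are treatment-emergent anyway (SAP 8.2.2). Only the by-period tables change.

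It can also be said that the intent is recoverable, since SAP 3.2.1 names a narrower term and the protocol separates the Taper. But the definition in 3.2.1 is explicit, and a programmer following it would include the Taper. A fallback written for missing visits should give the right answer when it is used.

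**Conclusion.** The rule is wrong as written, with limited scope. For a subject who misses the closing visit but still tapers, taper days are counted as Maintenance or Titration, which conflicts with the protocol's stable-dose Maintenance and separate Taper. For such a subject with Maintenance data, two effects are certain: the mean daily Maintenance dose is too low (12 becomes 8.6 or 10.3 mg/kg/day in the full 4-week taper examples) and the period's exposure is too long. The effect on seizure days is conditional on diary data and on a different seizure rate during the Taper, and its direction is unknown. The by-period TEAE table and the Treatment Period window can also shift.

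The number of subjects is not given and is probably small, so a material effect on the overall summaries should not be inferred. The illustrations assume adherence to the recommended taper, and the seizure example also assumes the rates. The outputs are descriptive, but one distorted value can be visible in a small age or syndrome group. The correction is inexpensive and should be made.

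**What to change.** In SAP 3.2.3, end each of the three fallbacks (Titration, Maintenance, Treatment) at the earlier of the last dose of LCM and the day before the start of the Taper. Define Taper start as the first dose reduction after the decision to discontinue, or after completion of Maintenance. State that a back-titration step during Titration is not a Taper start. Use the same definition in SAP 3.2.1 for the last dose during the Treatment Period, which removes the circularity.

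A dose decrease alone is not enough in Titration, because Protocol 7.2 allows unlimited back-titration and the SAP describes no taper flag on the dosing form. Where the dosing records do not show the Taper start, confirm it subject by subject at the Data Evaluation Meeting before database lock. In Maintenance this should be simpler, because the dose is meant to be stable.

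The cost is a SAP wording change, a matching change to the period derivation, and a short review item for probably few subjects. Administration start and stop dates are already used in SAP 8.4, so no new data collection is needed.

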### 3.2.4 Last Visit

The Last Visit for all assessments in SP0966 is the last non-missing assessment during the Treatment Period. This cannot be the same assessment as the baseline assessment. All scheduled and unscheduled assessments within this time period will be considered. Last Visit will be determined separately for each study procedure where Last Visit is mentioned within this document.

### 3.2.5 Age and age groups

The age (at enrollment) will be given in years (with 2 decimals) and will be derived with the following formula:

$$\text{Age (years)} = (\text{date of informed consent} - \text{date of birth}) / 365.25$$

Partial dates will not be completed. If it is not possible to calculate the age due to incomplete or missing date information the age as documented at Visit 1 will be used:

$$\text{Age (years)} = \text{years part of age in CRF} + (\text{month part of age in CRF} / 12)$$

If not stated otherwise, the following age groups will be used for the presentation of results:

- $\geq 1$  month to  $<4$  years,
- $\geq 4$  to  $<12$  years, and
- $\geq 12$  to  $<18$  years.

For the derivation of (markedly) abnormal values (see Sections 8.5, 8.6.1, and 8.6.2) the age at assessment will be used. This will be derived as follows:

- For subject with a complete date of birth, use the date of birth to calculate the age at the time of measurement.
- For subject with a partial date of birth with available information about year and month, use the first day of the month to impute the date of birth and use the imputed date of birth to calculate age at the time of measurement.
- For subject with a partial date of birth with available information about year only, use age as given in the eCRF and add the time between measurement and informed consent (ie, [date of measurement – date of informed consent] / 365.25).

### 3.3 Definition of Baseline values

Unless otherwise specified, Baseline will be based on the last nonmissing data collected prior to the first dose of LCM, ie, assessments on Visit 1 or Visit 2. It is possible that values measured on the day of first dose of LCM (Visit 2 [start of Titration Period]) are assigned to the Baseline Period for summary purposes.

### 3.4 Protocol deviations

Important protocol deviations are deviations from the protocol which could potentially have a meaningful impact on the primary or secondary safety outcomes or preliminary efficacy outcomes for an individual subject. The criteria for identifying important protocol deviations and the classification of important protocol deviations will be defined separately in the Specification of Protocol Deviations (SPD) document. To the extent feasible, rules for identifying protocol deviations will be defined without review of the data and without consideration of the frequency of occurrence of such deviations. Whenever possible, criteria for identifying important protocol deviations will be implemented algorithmically to ensure consistency in the classification of important protocol deviations across all subjects.

Important protocol deviations will be reviewed as part of the Data Evaluation Meeting (DEM) prior to database lock.

### 3.5 Analysis sets

The analysis set for subject disposition will be based on All Subjects Screened. Safety variables will be summarized for the Safety Set (SS); efficacy variables will be summarized for the Full Analysis Set (FAS). Select PK analysis may be based on the Pharmacokinetic Per-Protocol Set (PK-PPS). All other parameters will be summarized using the SS.

#### 3.5.1 Safety Set

The primary analysis set will be the SS and will include all enrolled subjects who take at least 1 dose of LCM.

### **3.5.2 Full Analysis Set**

The analysis set for the preliminary efficacy variables will be the FAS and will include all subjects in the SS having had a Baseline and at least 1 post-Baseline efficacy related assessment.

### **3.5.3 Pharmacokinetic Per Protocol Set**

The PK-PPS will consist of all subjects from the SS having provided at least 1 measurable post-dose plasma sample (with recorded sampling time) on at least 1 visit with documented LCM intake times.

### **3.6 Treatment assignment and treatment groups**

All subjects treated in this study receive LCM at doses ranging between 2mg/kg/day (or 100 mg/day) to 12 mg/kg/day (or 600 mg/day). Summaries will be presented based on total number of subjects and will generally not be differentiated by LCM dose. Where appropriate, LCM dose will be presented on subject data listings.

### **3.7 Center pooling strategy**

No data pooling strategies will be applied for analyses for this study. Unless otherwise stated, data from all sites will be combined and summarized collectively.

### **3.8 Coding dictionaries**

Medical history and AEs will be coded using the Medical Dictionary for Regulatory Affairs (MedDRA®) Version 16.1. Medications and therapies will be coded using the World Health Organization Drug Dictionary (WHO-DD) version September 2013. Medical procedures will not be coded.

### **3.9 Changes to protocol-defined analyses**

Not applicable.

## **4 STATISTICAL/ANALYTICAL ISSUES**

### **4.1 Adjustments for covariates**

Not applicable.

### **4.2 Handling of dropouts or missing data**

#### **4.2.1 Visit mapping in case of premature discontinuation**

Subjects who prematurely discontinue the study will be evaluated based on the data collected at each visit attended. For these subjects, the early termination visit will be mapped to the next scheduled visit, ie, the assessments documented at Visit 9/ET will be assigned to the next scheduled visit, for which the corresponding assessment is scheduled, following the last documented visit.

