^h Subject or caregiver (including parent/legal representative) will be asked how many seizures the subject has had over the past 4 weeks as a historical baseline.

ⁱ Ambulatory EEG to begin on the morning prior to the visit eg, the day before Visit 2, Visit 6, and Visit 9.

^j Height will only be recorded at study visits where a complete physical examination is performed. Height is not required at an Unscheduled Visit.

^k Two interpretable 12-lead ECG recordings will be performed approximately 20 to 30 minutes apart prior to any blood draws and vital sign assessments. The subject should rest in the supine position for approximately 5 minutes before the recordings and during the recordings, if possible. Recordings should be performed at least 15 minutes after the removal of scalp electrodes used for the 24-hour ambulatory EEG recordings at Visit 2, Visit 6, and Visit 9 or the ET Visit.

^l The assessment will only be required for subjects with an abnormal value (clinical chemistry, hematology, or endocrinology) or reading (ECG) at the previous clinic visit.

Table 5-1: Schedule of study assessments (Baseline Period, Titration Period, Maintenance Period, End of Study Period and Unscheduled Visit)

Assessments	Baseline Period (6 weeks)		Treatment (18 weeks)												End of Study Period			Unscheduled Visit ^a		
	Visit	TC 1	Titration Period (6 weeks)						Maintenance Period (12 weeks)						Taper Period (2-4 weeks) ^b		Safety Follow-Up (30 days)			
V1			TC 2	V3	TC 3	V4 ^c	V5 ^c	End of Titration V6	TC 4	V7	TC 5	V8	TC 6	V9/ ET ^d	TC 7 ^e	End of Taper Visit ^f		Safety FU Visit ^g	Safety FU TC ^g	At any time
Week in study	-6	-3	Day 1	1	2	3	4	5	6	8	10	12	14	16	18	19	20-22	22-24	24-26	

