13.4 Planned preliminary efficacy and other analyses

13.4.1 Preliminary efficacy analyses

Percent change in seizure days is calculated as the respective seizure days per 28 days during the Maintenance Period minus respective seizure days during Baseline per 28 days divided by Baseline days and then multiplied by 100. The respective seizure days per 28 days will be calculated as ([number of seizure days over the specified time interval] divided by [number of days in the interval]) multiplied by 28. Seizure days for all generalized seizure types will be based on the seizure diary.

Descriptive statistics to summarize the absolute and percent change in seizure days per 28 days from Baseline Period to the Maintenance Period will be presented for any generalized seizures reported and for each generalized seizure type.

The actual change in the count of generalized and 3Hz spike-wave discharges on 24-hour ambulatory EEG from Visit 2 to Visit 9 or Early Termination will be calculated and summarized descriptively.

Descriptive summaries will also be presented for the Clinical and Caregiver's Global Impression of Change, health care resource use, and the PedsQL.

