## **2.2.2 Efficacy variables**

### **2.2.2.1 Preliminary efficacy variables**

Variables used to assess preliminary efficacy will include:

- Change in days with absence seizures per 28 days from the Baseline Period to the Maintenance Period
- Change in days with myoclonic seizures per 28 days from the Baseline Period to the Maintenance Period
- Change in days with clonic seizures per 28 days from the Baseline Period to the Maintenance Period
- Change in days with tonic seizures per 28 days from the Baseline Period to the Maintenance Period
- Change in days with tonic-clonic seizures per 28 days from the Baseline Period to the Maintenance Period
- Change in days with atonic seizures per 28 days from the Baseline Period to the Maintenance Period

- Change in days with partial evolving to secondarily generalized seizures per 28 days from the Baseline Period to the Maintenance Period
- Percent change in days with any generalized seizures (absence, myoclonic, clonic, tonic, tonic-clonic, atonic, partial evolving to secondarily generalized) per 28 days from the Baseline Period to the Maintenance Period
- Percent change in days with absence seizures per 28 days from the Baseline Period to the Maintenance Period
- Percent change in days with myoclonic seizures per 28 days from the Baseline Period to the Maintenance Period
- Percent change in days with clonic seizures per 28 days from the Baseline Period to the Maintenance Period
- Percent change in days with tonic seizures per 28 days from the Baseline Period to the Maintenance Period
- Percent change in days with tonic-clonic seizures per 28 days from the Baseline Period to the Maintenance Period
- Percent change in days with atonic seizures per 28 days from the Baseline Period to the Maintenance Period
- Percent change in days with partial evolving to secondarily generalized seizures per 28 days from the Baseline Period to the Maintenance Period
- Changes in count of generalized spike-wave discharges on 24-hour ambulatory EEG from Visit 2 to Visit 9 or at Early Termination (ET)
- Changes in count of 3Hz spike-wave discharges (during waking hours) on 24-hour ambulatory EEG from Visit 2 to Visit 9 or at ET
- Clinical Global Impression of Change upon completion of the Maintenance Period (Termination) or at ET
- Caregiver's Global Impression of Change upon completion of the Maintenance Period (Termination) or at ET

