### **8.1 Primary safety variables**

#### **8.1.1 Generalized spike-wave discharges**

The actual values of generalized spike-wave discharges per interpretable hour on 24-hour ambulatory EEG as well as changes from Baseline will be summarized descriptively by visit.

Furthermore, a frequency table will be presented for the number of subjects with an increase of at least 30% and an increase of at least 50% at Visit 6 compared to Baseline.

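### EEG change from Visit 2 to Visit 9 or early termination is not produced as defined, because early-termination EEGs from Titration withdrawals are mapped to Visit 6; separately, threshold increases are tabulated only at Visit 6

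*SAP*

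**What the plan says.** **The variable.** Protocol 4.2 lists, among the preliminary efficacy variables, the change in generalized and in 3Hz spike-wave counts to Visit 9 or ET. Protocol 13.4.1 says that the change on "ambulatory EEG from Visit 2 to Visit 9 or Early Termination will be calculated and summarized descriptively". SAP 2.2.2.1 repeats both variables. The primary and secondary safety variables are different: they are the changes from Visit 2 to Visit 6 (Protocol 4.1.1 and 4.1.2).

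**The schedule.** Protocol Table 5-1 places EEGs at Visits 2, 6 and 9/ET only. Its footnote reads "Ambulatory EEG to begin on the morning prior to the visit eg, the day before Visit 2, Visit 6, and Visit 9", and Protocol 11.7.2 agrees.

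**The mapping.** SAP 4.2.1 states "For these subjects, the early termination visit will be mapped to the next scheduled visit" and then specifies that ET assessments are "assigned to the next scheduled visit, for which the corresponding assessment is scheduled, following the last documented visit".

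**The analysis.** SAP 8.1.1 says that values of generalized discharges "on 24-hour ambulatory EEG as well as changes from Baseline will be summarized descriptively by visit". It adds a frequency table of subjects with "an increase of at least 30% and an increase of at least 50% at Visit 6 compared to Baseline". SAP 8.2.1 does the same for 3Hz discharges. The exploratory table of decreases (SAP 8.3) is also limited to Visit 6.

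**What is absent.** SAP 9.1 has no EEG subsection. SAP 3.2.4 applies Last Visit only where a section names it, and no EEG section does. SAP 4.2.2 imputes seizure days but no other safety or preliminary efficacy variable. SAP 3.9 reports no changes to protocol-defined analyses.

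**The concern.** The protocol defines an end-of-treatment EEG result that includes every child with a Visit 9 or ET recording. The SAP keeps that variable in its list, but its mapping and by-visit rules yield a different one: a Visit 9 row restricted to children who got past the Titration Period. Seizure worsening serious enough to warrant stopping is a mandatory withdrawal reason (Protocol 6.3), so the omitted children may be the informative ones. Protocol 5.4 says the study is meant to identify syndromes in which lacosamide may provoke exacerbations.

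The second gap has a separate cause. Because SAP 8.1.1 and 8.2.1 fix the increase tables at Visit 6, a child whose discharges first rise past 30% or 50% during Maintenance appears in no threshold count.

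Elsewhere the SAP avoids both gaps. Seizure days carry Titration data forward for those who leave in Titration (4.2.2). Seizure increases of more than 30% and 50% are summarised for Titration and Maintenance (9.2). Laboratory values, vital signs and ECG have a Last Visit summary (8.5, 8.6.1, 8.6.2).

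**Working it through.** The plan gives no figure to reproduce: N = 50 has no formal calculation behind it, and no dropout rate is stated.

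**Step 1. Apply SAP 4.2.1 to the EEG schedule.** The rule picks the first of Visits 6 and 9 after the last documented visit.

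| Last documented visit | ET EEG is labelled |
|---|---|
| 2, 3, 4 or 5 | Visit 6 |
| 6, 7 or 8 | Visit 9 |

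**Step 2. Look for a rule that restores the Titration withdrawals at Visit 9.** Imputation does not cover EEG, Last Visit is not invoked, and Section 9 has no EEG analysis. None does.

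**Step 3. Size of the omission.** Assume 50 treated subjects, each with a Visit 9 or ET EEG, and let t be the number who withdraw in Titration (assumed). Visit 9/ET has n = 50; the SAP Visit 9 row has n = 50 − t.

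| t (assumed) | Visit 9/ET n | SAP Visit 9 n | Omitted, t/50 |
|---|---|---|---|
| 3 | 50 | 47 | 6% |
| 5 | 50 | 45 | 10% |
| 10 | 50 | 40 | 20% |
| 15 | 50 | 35 | 30% |

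Maintenance withdrawals remain in the row. With t = 10 and 5 Maintenance withdrawals, the 40 are 35 completers plus 5 ET EEGs.

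**Step 4. What the choice of set could do to a threshold table.** This is hypothetical, since the SAP plans no such table at Visit 9 and the protocol defines a change in count, not a proportion. Assume that 10% of subjects who reach Maintenance show an increase of at least 50% at their Visit 9/ET EEG, and a share w of Titration withdrawals do at their ET EEG. A Visit 9 row gives 10%. Visit 9/ET gives [w·t + 0.10·(50 − t)]/50. For t = 10 and w = 50%: (5 + 4)/50 = 18%.

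| t | w = 10% | w = 30% | w = 50% | w = 80% |
|---|---|---|---|---|
| 3 | 10.0% | 11.2% | 12.4% | 14.2% |
| 5 | 10.0% | 12.0% | 14.0% | 17.0% |
| 10 | 10.0% | 14.0% | 18.0% | 24.0% |
| 15 | 10.0% | 16.0% | 22.0% | 31.0% |

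If withdrawals worsen at the same rate as the others, the proportions do not differ.

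**Step 5. Period without a threshold count.** Maintenance is 12 of the 18 treatment weeks: 12/18 = 67%.

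**The case against.** The best defence is that little is lost. Titration ET EEGs are relabelled, not discarded: they enter the Visit 6 summary and the Visit 6 increase table, which serves the Visit 2 to Visit 6 safety variables. The protocol asks for threshold counts at no visit, so placing these SAP additions at the primary time point breaks no commitment. Exacerbation is also examined through seizure days, seizure increases by period and syndrome, and adverse events. All of this stands, and it limits the weight of the point. It does not supply the declared Visit 9 or ET variable.

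Stronger readings that a reader might infer are not supported:

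- *The Visit 9 row contains survivors only.* ET EEGs from Maintenance withdrawals are mapped to Visit 9 and stay in.
- *Later worsening goes unseen.* Only the threshold counts are missing. Changes at Visit 9 are summarised, with minimum and maximum, and individual data are listed (SAP 3.1).
- *The primary EEG variable is undermined.* The mapping keeps Titration withdrawals in it. Their recordings may come before Week 6 and at lower doses, but EEGs at the actual Visit 6 also span a range of doses by design.
- *Mapped ET EEGs are off-drug recordings.* The documents give no delay between last dose and ET EEG, and taper medication is dispensed at Visit 9/ET (Protocol 8.3.4). Some subjects may stop without taper, but how many is not stated.

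**Conclusion.** The point holds in two parts of different weight. First, the change to Visit 9 or ET, for both generalized and 3Hz discharges, is not produced as the protocol and the SAP's own variable list define it, and SAP 3.9 does not say so. This follows from the rules alone and needs no assumption beyond at least one Titration withdrawal with an ET EEG. Second, the absence of a threshold count after Visit 6 is a gap worth closing, not a departure from the protocol.

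The size cannot be fixed from the documents. The proportions in Step 4 rest on assumed rates and show direction only. The affected variables are preliminary efficacy variables in a descriptive, single-arm study; the primary Visit 6 result is not at risk. The change should be made because it is cheap and restores a declared variable.

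**What to change.** In SAP 8.1.1 and 8.2.1, or in a new EEG subsection of 9.1:

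1. Add a Visit 9/ET row for values and changes from Baseline, using each subject's Visit 9 or ET EEG regardless of the period of withdrawal.
2. Repeat the tables of increases of at least 30% and 50% at Visit 9/ET and for any post-Baseline EEG.
3. Keep the present Visit 6 row, mapped ET EEGs included, as the primary presentation. Limiting it to actual Visit 6 recordings would remove Titration withdrawals from the primary safety row, so that belongs, if anywhere, in an optional sensitivity line.
4. If the sponsor prefers the current method, declare it in SAP 3.9 as a change to the protocol-defined analysis.

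The cost is some SAP wording and a few table rows from recordings already planned. The Visit 9/ET figures may look less favourable than the Visit 9 figures.
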